### Imaging as a biomarker for patients selection

Imaging using multi-modal MR or CT is the most likely biomarker for selection of patients for thrombolytic therapy. The theoretical construct of the penumbra defined by the difference between (a) tissue-at-risk or destined for infarction but not already infarcted and (b) tissue that is already irreversibly infarcted, is clear. There is consensus in the stroke community and little doubt that this is a correct conceptual way of thinking about the problem.

However, it is a simplification of reality because the line between (a) and (b) is not a straight black line border. It is gray. The operational definitions of what is irreversibly infarcted and what is potentially salvageable have proven to be very challenging to delineate. Thus, measurement errors using either multi-modal CT or multi-modal MRI have proven to be major barriers in using the mismatch hypothesis. In addition, acquisition and analysis of the data from the multi-modal imaging can be time consuming which itself can influence outcome. There is a great need to move very rapidly to get treatment started. Any trade-off of time to gather advanced information must be worth the expense in the treatment delay. Currently, it is our belief that this is not the case.

Two trials, assessing the novel thrombolytic agent desmoteplase, have failed to show that selecting patients using a mismatch paradigm is a useful technique for defining a thrombolysis eligible cohort. However, much has been learned and cohort analysis of the EPITHET study and the DEFUSE studies have shown that certain populations can be selected as ideal or non-ideal for treatment. For example, DEFUSE has further confirmed the CT literature, that patients with very large burdens of infarction (>100cc volume defined by DWI) do not benefit from recanalization therapy.

The key imaging data that are needed to make a treatment decision then are as follows (framed as questions):

- 1) Is the inclusive diagnosis a moderate to severe ischemic stroke (defined as >5 on the NIHSS)? The corollary is that ischemic stroke is not a diagnosis of exclusion.
- 2) Is there extensive infarction defined as tissue hypodensity on non-contrast CT scan (defined on the basis of ASPECTS scoring system) or extensive ADC restriction/DWI lesion volume (>100cc) on MR?
- 3) Where is the location of the arterial occlusion defined by non-invasive imaging?
- 4) Is the arterial occlusion amenable to safe and fast recanalization using endovascular means or combined intravenous thrombolysis plus endovascular treatment?

We have solved these questions using CT scanning and can gather and interpret these data in <10 minutes. Using the ASPECTS score, we can exclude extensive infarction. Using CT angiography, we can gain detailed information on the location of occlusion and the burden of thrombus. Further the CTA (from arch to vertex) can aid the interventionist in pre-planning navigation from the aortic arch to the thrombus. The pattern of collaterals is also discernible from CTA; patients with absent or very poor collaterals do not benefit from therapy, simply because it cannot be brought to bear in a timely enough fashion to prevent significant infarction.

Thus, we adopt a fast image acquisition “good scan (small core), occlusion” model of patients selection and believe that this group of patients are the best ones to show a large magnitude of effect and provide the proof that endovascular therapy is the right treatment for patients with stroke. A future trial might examine expanding this population of patients.

## Study Design

This will be a Phase 3 randomized, open-label with blinded outcome evaluation, parallel group design study with blinded outcome evaluation.

## Outcomes

### Primary Outcome

A shift or one or more categories (proportional odds analysis) on the modified Rankin scale at 90 d.

### Secondary Outcome

The following outcomes will be assessed as the proportion of patients who achieve each score. We will also examine each score as raw score comparisons. Where appropriate, we will examine the scores as continuous measures or binned at logical groupings (eg. quartiles).

- (i) NIHSS score of 0-2 at 30 days and 90 days
- (ii) mRS score of 0-2 at 30 days and 90 days
- (iii) NIHSS score at 90 days
- (iv) mRS score at 90 days
- (v) BI score at 90 days
- (vi) BI shift at 90 days
- (vii) Health Utilities index at 90 days
- (viii) EQ-5D (EuroQoL) at 90 days
- (ix) Fast cognitive battery using the following subscales at 90 days
  - a. Trail-making A & B
  - b. MoCA
  - c. Boston Naming test
  - d. Sunnybrook hemi-neglect battery
- (x) NIHSS score at 24 hours
- (xi) NIHSS score at 48 hours
- (xii) NIHSS score at discharge
- (xiii) Recanalization of the target arterial occlusive lesion (TICI 3 flow) at the end of the procedure
- (xiv) TICI 3 score at the end of the procedure
- (xv) miFUNCTION scale
- (xvi) Economic analysis – cost effectiveness.

(xvii) Deferral of consent survey

### Safety Outcomes

- (i) symptomatic intracranial hemorrhage
- (ii) major bleeding due to femoral artery access complications including groin hematoma, retroperitoneal hematoma [definition]
- (iii) contrast nephropathy
- (iv) total radiation dose (CT, CTA, angiography)
- (v) malignant MCA infarction
- (vi) hemicraniectomy

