|                                | 
according to the current standard of care. Subjects are required to return to clinic on Days 30 & 90 for end-of-study procedures.
  |
| Evaluation Criteria     | 
Safety Analysis: incidence of serious adverse events associated with the treatment protocol. These include:
 
 
a. vessel perforation
 
b. symptomatic ICH
 
c. iatrogenic vessel dissection
 
d. retroperitoneal hematoma
 
e. femoral neuropathy at the groin puncture site
 
f. major extracranial bleeding
 
 
Primary Efficacy Outcome:
 
A shift or one or more categories (proportional odds analysis) on the modified Rankin scale.
 
Key Secondary Outcomes:
 
NIHSS 0-2
 mRS 0-2
 Mortality at 90 days
 EQ-5D (EuroQoL)
 Cognitive outcomes (Trailmaking A, B; MoCA; Boston Naming test; Sunnybrook hemi-spatial neglect battery)
 Barthel Index > 90 (<math>\geq 95</math>)
 Barthel Index shift analysis (ordinal logistic regression)
 miFUNCTION score
 Economic (cost-effectiveness) analysis
 Qualitative evaluation of the waiver/deferral of consent process
 |
| Training Considerations | 
 
1. Optimisation of NCCT scanning protocols and training of CT scanner technicians at each site will be undertaken by the study personnel.
 
2. Training of investigators on the ‘tips and tricks’ of endovascular thrombectomy. Training of the endovascular team (angio suite nurses and technologists) to reduce CT-to-recanalization times.
 
3. Study discipline and rigour on randomization of all patients who might fit these criteria. Given the possibility of the “loss of equipoise” in an active procedural trial, it is critical to get recruitment completed fast and to maintain
 
   |

|                                   |   |
|-----------------------------------|---|
|                                   | study-wide discipline in subject enrolment. Patients must not cross over.   |

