### Process and Quality Outcomes

- (i) CT-to-groin puncture time (“Picture-to-puncture”)
- (ii) CT-to-recanalization time
- (iii) Aspiration pneumonia
- (iv) Rate of use of general anesthesia
- (v) Rate of symptomatic deep venous thrombosis / pulmonary embolism
- (vi) Proportion of patients with any SAE per site
- (vii) Qualitative Interview to assess the process of waiver/deferral of consent.

Symptomatic intracranial hemorrhage defined as new intracranial hemorrhage (ICH, SAH, IVH, SDH) associated with clinical evidence of neurological worsening, in which, the hemorrhage is judged to be the most important cause of the neurological worsening. Clinical worsening will be guided by the NIHSS score of a minimum of 2 or more points different from baseline.

Major extracranial hemorrhage defined as life threatening, resulting in hemodynamic compromise or hypovolemic shock, requiring inotropic support or other means to maintain cardiac output, requiring blood transfusion of more than 2 units of packed red blood cells, or associated with a fall in hemoglobin greater than or equal to 5 g/L.

Contrast nephropathy will be defined as any rise of the serum creatinine by 50% or more between the baseline pre-treatment level and that measured at 24h post-treatment.

Total radiation dose will be measured in mSv and recorded directly from the CT scanner. Dose-length product will be recorded directly from the CT scanner.

Malignant MCA infarction will be defined as any large infarction with mass effect observed on imaging where treatment (medical or surgical) is required for the treatment of mass effect.

Hemicraniectomy will be defined as that surgical procedure used to decompress the swollen hemisphere.

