### Study Interventions

Patients will be randomized to routine stroke care governed by current guidelines (control group) or to emergency endovascular revascularization. Endovascular mechanical revascularization may be undertaken with any currently available and approved device or paradigm and used according to the manufacturers specifications for use.

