### Endovascular Intervention

Regulatory agency approved devices may be used (stentriever, aspiration devices). Endovascular intervention may include the administration of intra-arterial thrombolytic (eg. tPA) and the use of balloon angioplasty or guidewire manipulation of thrombus. Endovascular intervention may include direct aspiration of the thrombus through a large bore access catheter. It is not recommended that permanent stents be left in the intracranial circulation or in the internal carotid artery. Guidelines for recommended approaches to endovascular revascularization are reported in Appendix 1.

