### Guidelines-based Care – the Control Group

Acute stroke patients should receive the best standard of care according to national guidelines. The model will be the Canadian best practices guidelines for acute stroke care. These are very similar to the guidelines of the American Stroke Association and the European Stroke Organization.

In brief, we expect –

- A. Patients who are appropriate candidates for intravenous thrombolytic therapy within 4.5 hours of defined stroke onset to get rapidly administered IV therapy.
- B. All patients to be managed urgently with attention to physiology. Airway, breathing and circulation first. Fluids – usually normal saline - should be administered as most patients are slightly hypovolemic. Blood pressure should not be aggressively treated other than to guidelines to allow thrombolytic therapy.
- C. All patients should be managed on a stroke unit which should include early mobilization, early rehabilitation, DVT prophylaxis, swallowing assessment and prevention of aspiration pneumonia, NG feeding as appropriate and delayed (up to 4 weeks) placement of PEG tubes in the uncommon instance that these are needed.
- D. All patients should receive ASA therapy (minimally) within the first 48h of stroke but after a day +1 brain image shows no evidence of hemorrhage.
- E. Patients should not receive intravenous unfractionated heparin.
- F. All patients should be thoroughly investigated to sort out the mechanism of stroke and appropriate stroke prevention strategies implemented. There is little use in working very hard on a technical and aggressive approach to acute stroke if it is to be undone on day +10 with a recurrent embolus because a patient has not been effectively treated for a preventable cause of stroke.
- G. All patients should have relevant and appropriate stroke rehabilitation therapy.

In summary, we expect that all patients should have excellent, guideline based stroke care through the full 90 days. These are outlined in our Guidance Document for Best Medical Care.

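### Major bleeding is limited to femoral access in the listed safety outcomes but covers any site in the synopsis and in the protocol's own definition, so the listed outcome cannot compare the arms

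*Protocol*

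**What the plan says.** Four places in the protocol bear on this outcome.

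- **Protocol synopsis, Evaluation Criteria.** The safety analysis is framed as "incidence of serious adverse events associated with the treatment protocol". Item f is "major extracranial bleeding", with no site or cause attached. Item d, "retroperitoneal hematoma", stands as a separate entry.
- **Safety Outcomes, item (ii).** The listed outcome is "major bleeding due to femoral artery access complications including groin hematoma, retroperitoneal hematoma [definition". The closing bracket follows and no definition was inserted.
- **Definitions printed under Process and Quality Outcomes.** The second one begins "Major extracranial hemorrhage defined as life threatening, resulting in hemodynamic compromise or hypovolemic shock". It goes on to accept inotropic or similar support, transfusion of more than 2 units of red cells, or a haemoglobin fall of at least 5 g/L. Every limb concerns severity; none concerns site or cause.
- **List of Expected Adverse Events.** The expected serious events are set equal to the safety outcomes, so whatever item (ii) means is carried over.

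On treatment, the Study Interventions section says: "Patients will be randomized to routine stroke care governed by current guidelines (control group) or to emergency endovascular revascularization". The control-group section expects "Patients who are appropriate candidates for intravenous thrombolytic therapy within 4.5 hours of defined stroke onset to get rapidly administered IV therapy", and the expected population also includes endovascular patients given intravenous tPA. For the endovascular arm, "Endovascular intervention may include the administration of intra-arterial thrombolytic (eg. tPA").

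**The concern.** A randomised trial of an invasive procedure should be able to say whether major bleeding is more frequent with the procedure than without it. That needs an outcome that a patient in either arm can have. Item (ii) is tied to a cause that the protocol introduces in only one arm, so it behaves as a procedural complication rate.

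Bleeding away from the groin is relevant in this trial. The expected population includes patients on anticoagulants, with a raised INR, or with recent surgery or bleeding. Intravenous thrombolysis may be given in both arms, and the endovascular arm may add intra-arterial thrombolytic. If item (ii) is followed literally, such bleeds have no place in the named outcome. If the synopsis is followed, they do. Two analysts working from the same protocol could tabulate different events under the same label.

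**Working it through.** The protocol gives no extracranial bleeding rate and no calculation for this outcome, so there is no figure to reproduce. The check is a comparison of texts, followed by simple algebra on what the difference does to the contrast.

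**Step 1: classify the same bleed under each text.**

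| Bleed | Synopsis item f | Definition | Safety Outcomes (ii) |
|---|---|---|---|
| Gastrointestinal bleed needing more than 2 units, either arm | event | event | not an event |
| Retroperitoneal haematoma from groin puncture, with shock | event (also item d) | event | event |
| Groin haematoma with no shock, support or transfusion and a haemoglobin fall under 5 g/L | severity not stated | not an event | undecided, because the marker is unfilled |

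The first row is the contradiction. The third shows that item (ii) has no severity threshold of its own.

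**Step 2: can the definition rescue item (ii)?** The six definitions run in the same order as the six listed safety outcomes: symptomatic intracranial haemorrhage, major extracranial haemorrhage, contrast nephropathy, radiation dose, malignant MCA infarction, hemicraniectomy. The second definition therefore sits in the slot for item (ii). Two readings are possible:

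- The definition replaces the label. The outcome is then any-site and agrees with synopsis item f, but the wording of item (ii) is wrong.
- The definition supplies only the severity threshold, and the femoral cause remains. Item (ii) then conflicts with synopsis item f.

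Under either reading one text has to change.

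**Step 3: effect on the contrast if item (ii) is followed literally.** Let a be the access-bleed risk in the endovascular arm (taken as 0 in controls for simplicity), b the non-access risk common to both arms, and d any extra non-access risk in the endovascular arm.

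- Item (ii): a against 0, so the difference is a and the ratio is undefined.
- Any site: a + b + d against b, so the difference is a + d and the ratio is (a + b + d)/b.

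The two differences disagree by exactly d. If d = 0 the risk difference is unaffected.

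**Step 4: illustration with assumed rates.** Only the arm size comes from the protocol: a maximum of 500 patients randomised 1:1, so 500/2 = 250 per arm. Assume a = 1% to 3%, b = 1% to 3%, d = 0 to 2 points.

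| a | b | d | Item (ii), events | Any site, events | Difference, (ii) | Difference, any site |
|---|---|---|---|---|---|---|
| 1% | 1% | 0 | 2.5 v 0 | 5 v 2.5 | 1 point | 1 point |
| 1% | 1% | 2 | 2.5 v 0 | 10 v 2.5 | 1 point | 3 points |
| 3% | 3% | 0 | 7.5 v 0 | 15 v 7.5 | 3 points | 3 points |
| 3% | 3% | 2 | 7.5 v 0 | 20 v 7.5 | 3 points | 5 points |

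For example, in the last row 250 × (0.03 + 0.03 + 0.02) = 20 and 250 × 0.03 = 7.5. The table shows the mechanism. It says nothing about the rates in this trial.

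**The case against.** The strongest reply is that the body of the protocol is ambiguous and does not settle on a femoral-only outcome: the any-site definition sits in the slot for item (ii) and may be what the marker was waiting for. This stands. The body is inconsistent between a label and its definition, and it would be wrong to say that it uniformly restricts the outcome to the groin. The label still contradicts the synopsis.

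A reader might infer that controls can have no event at all under item (ii). The documents do not support that. Patients with stroke after elective coronary angiography may be eligible, carotid revascularization is expected in relevant patients, and a control could cross over. Any of these might involve femoral access, although the route is not stated. Near zero by design is as far as the text goes.

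A reader might also infer that the wording conceals an excess of bleeding, or loses drug-related bleeds in the endovascular arm only. Neither follows. Non-access bleeds fall outside item (ii) in both arms. Those that are life threatening or prolong hospital stay are serious adverse events, which a safety committee adjudicates, and the DSMB reviews the complete safety data at the end of the study. What goes missing is a line in the named outcome, not the data. One gap remains: adjudication covers safety outcomes and serious events, so a non-access bleed that meets only the haemoglobin limb and is not serious would be recorded as an adverse event without adjudication.

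Two further replies have some weight. The synopsis list is framed around treatment-associated events and contains several procedural items, so listing access-site bleeding is reasonable in itself. That is a reason to keep it as a subset; it does not explain why item f is unrestricted and separate from item d. The detailed safety analysis is also left to a statistical analysis plan. That plan would still have to choose between two incompatible outcomes in the protocol.

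**Conclusion.** The concern holds as an internal inconsistency that should be corrected. Synopsis item f and the severity definition cover major extracranial bleeding at any site. Listed item (ii) covers only bleeding from femoral access and has an unfilled marker, and the expected-event list inherits that wording. Followed literally, item (ii) gives close to a one-arm procedural rate and cannot answer whether major bleeding differs between the randomised groups.

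The size cannot be stated from the documents. The risk difference is distorted by the between-arm difference in non-access bleeding and by nothing else; if there is none, only the counts and the ratio change. The conclusion rests on controls having no femoral puncture under the protocol, and on item (ii) being read by its own words. The retention of serious bleeds in the adjudicated data keeps this a correction to an outcome definition rather than a gap in safety surveillance.

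**What to change.** - Reword Safety Outcomes item (ii) as major extracranial haemorrhage at any site, assessed in both arms, using the definition already given under Process and Quality Outcomes.
- Report femoral-access bleeding (groin and retroperitoneal) as a named subset.
- Delete the unfilled marker.
- Bring the synopsis, the Safety Outcomes list, the definition and the List of Expected Adverse Events into agreement.
- Before applying the definition to both arms, check its haemoglobin limb, including the unit. A fall of 5 g/L is 0.5 g/dL and stands beside limbs such as shock and transfusion of more than 2 units. A limit that small could classify many minor falls as major bleeding.

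The cost is mainly wording. Serious bleeds are already reported and adjudicated, and a blood count is scheduled at baseline and at 24 hours in all patients. Non-serious bleeds that meet the definition would need to be picked out of the adverse event records and sent for adjudication. The downside is a higher reported bleeding count in both arms, and how much higher depends on how the haemoglobin limb is settled.

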### Process and Quality Outcomes

- (i) CT-to-groin puncture time (“Picture-to-puncture”)
- (ii) CT-to-recanalization time
- (iii) Aspiration pneumonia
- (iv) Rate of use of general anesthesia
- (v) Rate of symptomatic deep venous thrombosis / pulmonary embolism
- (vi) Proportion of patients with any SAE per site
- (vii) Qualitative Interview to assess the process of waiver/deferral of consent.

Symptomatic intracranial hemorrhage defined as new intracranial hemorrhage (ICH, SAH, IVH, SDH) associated with clinical evidence of neurological worsening, in which, the hemorrhage is judged to be the most important cause of the neurological worsening. Clinical worsening will be guided by the NIHSS score of a minimum of 2 or more points different from baseline.

Major extracranial hemorrhage defined as life threatening, resulting in hemodynamic compromise or hypovolemic shock, requiring inotropic support or other means to maintain cardiac output, requiring blood transfusion of more than 2 units of packed red blood cells, or associated with a fall in hemoglobin greater than or equal to 5 g/L.

Contrast nephropathy will be defined as any rise of the serum creatinine by 50% or more between the baseline pre-treatment level and that measured at 24h post-treatment.

Total radiation dose will be measured in mSv and recorded directly from the CT scanner. Dose-length product will be recorded directly from the CT scanner.

Malignant MCA infarction will be defined as any large infarction with mass effect observed on imaging where treatment (medical or surgical) is required for the treatment of mass effect.

Hemicraniectomy will be defined as that surgical procedure used to decompress the swollen hemisphere.

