## List Abbreviations

|            |  |
|------------|--|
| aPTT       | Activated Prothrombin Time   |
| AE         | Adverse Event  |
| ASA        | Acetylsalicylic Acid   |
| ASPECTS    | Alberta Stroke Program Early CT Score  |
| BI         | Barthel Index  |
| BP         | Blood Pressure   |
| CBC        | Complete Blood Count   |
| CBV        | Cerebral Blood Volume  |
| miFUNCTION | Comprehensive Hierarchical Evaluation of Disability based on Activity limitations  |
| CRF        | Case Report Form   |
| CRU        | Clinical Research Unit   |
| CSC        | Comprehensive Stroke Centre  |
| CT         | Computed Tomography  |
| CTA        | Computerized Tomographic Angiography   |
| CTP        | Computerized Tomographic Perfusion   |
| DBP        | Diastolic Blood Pressure   |
| DSMB       | Data and Safety Monitoring Board   |
| DWI        | Diffusion Weighted Imaging'  |
| DVT        | Deep Vein Thrombosis   |
| ECG        | Electrocardiogram  |
| eCRF       | Electronic Case Report form  |
| ED         | Emergency Department   |
| EDC        | Electronic Data Capture  |
| EMEA       | European Medicines Agency  |
| EQ-5D      | A standardized assessment instrument (developed by the EuroQol Group) that provides a simple descriptive measure of health outcome |
| FDA        | Food and Drug Administration   |
| FLAIR      | Fluid Attenuated Inversion Recovery  |
| g/L        | Grams per Litre  |
| GRE        | Gradient Echo MRI  |
| HIPAA      | Health Insurance Portability and Accountability Act  |
| IA         | Intra-arterial   |
| ICH        | Intracranial Hemorrhage  |
| ICH-GCP    | International Conference on Harmonization Good Clinical Practice   |
| INR        | International Normalized Ratio   |
| IRB        | Institutional Review Board   |
| IA         | Intra-arterial   |
| ICA        | Internal Carotid Artery  |
| ICH        | Intracerebral Hemorrhage   |
| IOML       | Inferior Orbitomeatal Line   |

|       |  |
|-------|--|
| IVH   | Intraventricular Hemorrhage                                |
| IV    | Intravenous  |
| MCA   | Middle Cerebral Artery                                     |
| MI    | Myocardial Infarction                                      |
| MIPS  | Maximum Intensity Projections                              |
| MoCA  | Montreal Cognitive Assessment                              |
| MOP   | Manual of Procedures                                       |
| MR    | Magnetic Resonance   |

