## Clinical Management of the Patient

It is expected that subjects will receive the best usual standard of stroke unit care. All subjects are expected to be admitted to hospital as part of routine standard of care.

It is expected that all subjects will undergo a routine work-up for the mechanism of their stroke and be treated appropriately and definitively. This is critically important because subjects who have an excellent early recovery are at the highest risk of early recurrent stroke. We wish to prevent recurrent stroke from confounding the 30-day and 90-day clinical outcome such that patients who are well at discharge remain that way for the duration of the 90-day follow-up period.

We expect the following preventive care. Relevant patients with atrial fibrillation should be anti-coagulated. Patients with symptomatic carotid artery stenosis should undergo carotid revascularization early and definitely within 2 weeks of stroke onset. Risk factors, including hypertension, elevated cholesterol, diabetes mellitus, tobacco smoking, should be treated appropriately and aggressively according to current standards of care.

We expect patients to receive adequate hydration to prevent renal complications. Patients will receive intravenous radio-contrast media for CT angiography and in half the study population for endovascular intervention. While this medication is generally extremely safe in stroke patients, simple hydration can prevent renal complications, particularly among patients with baseline borderline renal function and among those with diabetes mellitus. Further, patients with ischemic stroke are generally slightly hypovolemic at baseline. We recommend use of intravenous normal saline (0.9% saline) infusion at 1.5 – 2.0 cc/kg/h until the subject is eating and drinking safely and well. Therefore, for the typical subject this will mean IV NS at 75-125 cc/h overnight only. We do not recommend the use of bicarbonate solutions or N-acetyl-cysteine solutions for renal protection.

For patients that are disabled from their stroke and require a longer in-patient stay and/or rehabilitation, it is expected that they will receive standard stroke unit care to prevent complications. These include:

- DVT prophylaxis for patients who are bed-bound or primarily bed-bound
- Swallowing assessments and prevention of aspiration pneumonia

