### **Evaluations Following Randomization**

Creatinine and CBC are collected at 24 ( $\pm$  6 hours). An ECG will be completed at 24 ( $\pm$  6 hours). Subjects randomized to the control arm (best medical management) will have a CTA COW completed at 2-8 hours following randomization. If there is a situation that arises where a subject randomized to the endovascular group does not have a final cerebral angiogram performed, that patient should have a 2-8h CTA to evaluate recanalization. All subjects will undergo a follow-up NCCT scan or brain MRI (including a minimum of diffusion-weighted imaging [DWI], gradient-echo [GRE], FLAIR, and intracranial MR angiography [MRA]) at 24 hours ( $\pm$  6 hours) from the time of randomization. All subjects will have an historical mRS and miFUNCTION scale scores evaluated at 24 hours, 30 days ( $\pm$  7 days) and 90 days ( $\pm$  7 days). All subjects also undergo a NIHSS assessment at 2-8h (at the time of CTA), 24 hours ( $\pm$  6 hours), 48 hours ( $\pm$  6 hours), and 5 days or discharge, whichever comes first, 30 days ( $\pm$  5 days) and 90 days ( $\pm$  7 days). Where the deferral of consent process is approved and in use, all subjects who are enrolled using this process should have the deferral of consent survey completed in the 1-5d window and at 90 days. A mRS will be completed at 30 days ( $\pm$  5 days) and 90 days ( $\pm$  7 days). The Barthel Index will be completed at 30 days ( $\pm$  5 days) and 90 days ( $\pm$  7 days). The EQ-5D will be completed at 30 days ( $\pm$  5 days) and 90 days ( $\pm$  7 days). A cognitive battery using the following subscales will be completed at 90 days ( $\pm$  7 days): Trailmaking A & B, MoCA, Boston Naming test and Sunnybrook hemi-neglect battery. At minimum 90-day outcomes assessments on the mRS, NIHSS and BI should be conducted by an evaluator blind to the acute treatment. It is preferred if all 90-day outcome assessments are conducted by a blinded evaluator.

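### A haemoglobin fall of only 5 g/L is enough to grade an extracranial bleed as major, so minor access-site bleeds could be counted as major, mainly in the endovascular arm

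*Protocol*

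**What the plan says.** The definition stands in the Protocol under Process and Quality Outcomes, after the numbered list. It opens "Major extracranial hemorrhage defined as life threatening, resulting in hemodynamic compromise or hypovolemic shock", continues through inotropic or similar support and "requiring blood transfusion of more than 2 units of packed red blood cells", and ends with an alternative: a bleed "associated with a fall in hemoglobin greater than or equal to 5 g/L". The criteria are joined by *or*, so any one suffices. The List Abbreviations expands the unit as "Grams per Litre", so the printed threshold is 0.5 g/dL.

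Three other parts of the Protocol bear on it:

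- **Haemoglobin is measured in everyone.** A CBC is part of the baseline blood work, and under Evaluations Following Randomization "Creatinine and CBC are collected at 24" hours, plus or minus 6.
- **Fluids are recommended for everyone.** Clinical Management of the Patient states that "patients with ischemic stroke are generally slightly hypovolemic at baseline" and recommends saline; "for the typical subject this will mean IV NS at 75-125 cc/h overnight only".
- **The outcome appears under different labels.** The synopsis lists "major extracranial bleeding" in its Safety Analysis. Safety Outcomes, item (ii), lists major bleeding from femoral access complications and leaves a bracketed placeholder where its definition should stand.

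**The concern.** Where criteria are alternatives, the mildest one sets the effective definition. Here it is much milder than the rest: a small change on a routine blood count sits beside shock, inotropes and transfusion of more than 2 units. Because fluids alone may supply the fall, the criterion would add little once any bleed has been noted, and it would not separate major from minor bleeding.

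The effect is unlikely to be equal between arms. Hydration is recommended in both, but the criterion needs a bleed to act on. Groin puncture is how endovascular treatment starts (inclusion criterion 8), and it is not part of control care. Small groin haematomas should therefore arise mainly in the endovascular arm, and promoting them to major would raise that arm's rate. This matters because safety is a secondary objective (synopsis), the target complication rate is under 1% (Speed of Intervention), and the DSMB reviews the safety profile.

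**Working it through.** The threshold is a definition. No sample size, power or alpha depends on it, so there is no plan figure to reproduce. The check is whether 5 g/L can mark a major bleed.

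**Inputs from the Protocol:** threshold 5 g/L; saline 75-125 cc/h overnight; CBC at baseline and at 24 hours.

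**Assumptions, none given in the Protocol:** baseline haemoglobin (Hb) 130-150 g/L; blood volume (BV) 5 L, varied over 4-6 L in step 2; overnight taken as 12 hours; 10-25% of the saline still in the circulation.

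**1. Relative size.** 5/150 = 3.3% and 5/130 = 3.8% of baseline. At 5 L, the same fraction of blood volume is 5,000 × 5/150 = 167 mL to 5,000 × 5/130 = 192 mL.

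**2. Retained fluid needed for a given fall T without bleeding.** V = BV × T/(Hb − T). For T = 5:

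- Smallest: 4 × 5/145 = 0.138 L.
- Largest: 6 × 5/125 = 0.240 L.

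**3. Fall expected from the recommended saline.** Volume given is 75 × 12 = 900 mL to 125 × 12 = 1,500 mL. Fall = Hb × v/(BV + v), where v is the retained volume and BV = 5 L. Results in g/L:

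| Rate | Retained volume | Hb 130 | Hb 140 | Hb 150 |
|---|---|---|---|---|
| 75 cc/h | 90 mL (10%) | 2.3 | 2.5 | 2.7 |
| 75 cc/h | 180 mL (20%) | 4.5 | 4.9 | 5.2 |
| 75 cc/h | 225 mL (25%) | 5.6 | 6.0 | 6.5 |
| 125 cc/h | 150 mL (10%) | 3.8 | 4.1 | 4.4 |
| 125 cc/h | 300 mL (20%) | 7.4 | 7.9 | 8.5 |
| 125 cc/h | 375 mL (25%) | 9.1 | 9.8 | 10.5 |

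The range is 2.3 to 10.5 g/L. No cell at 10% retained reaches 5 g/L; every cell at 25% does. Dilution alone can therefore meet the threshold, but not in every scenario. Where it falls short, it still supplies part of the fall, and a small bleed could supply the rest.

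**4. Does this identify the intended value?** Using the formula in step 2 with BV = 5 L, a fall of 20 g/L needs 5 × 20/130 = 0.77 L to 5 × 20/110 = 0.91 L retained. A fall of 50 g/L needs 5 × 50/100 = 2.5 L to 5 × 50/80 = 3.1 L. Both exceed the largest retained volume in the table, 0.375 L. Either threshold would be out of reach of dilution on these assumptions, so the calculation does not point to one of them.

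**The case against.** The strongest reply is that the definition is of a haemorrhage. The haemoglobin criterion grades a bleed that has occurred, and under Adverse Event Reporting and Review a committee adjudicates every safety outcome and decides its classification. That stands against a tempting stronger reading: that the outcome would count many patients who never bled. They would be counted only if the criterion were applied mechanically to the 24-hour CBC. A share of such patients can be calculated, but only by assuming how haemoglobin changes in people who do not bleed. With a normal model, 1 − Φ((5 − mean)/SD), a mean fall of 0-10 g/L and an SD of 4-10 g/L give 11% to 89%. The Protocol supplies neither input, and the result is a frequency of haemoglobin falls, not of adjudicated bleeds.

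Adjudication does not remove the narrower problem. The Protocol has no other written criterion for major extracranial bleeding, and the placeholder in Safety Outcomes (ii) offers no alternative. If the committee follows the text, minor bleeds become major; if it overrides the text, the outcome is no longer the one specified.

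A reader might also infer that g/dL was meant, a tenfold slip. That is possible, but nothing in the Protocol establishes it.

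Nor do the documents support an arm difference caused by extra fluid or contrast. Controls also receive contrast, at the baseline CTA and again at the 2-8 hour CTA. The arm difference argued here rests only on femoral puncture.

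**Conclusion.** The point holds as a fault in classification. As printed, the haemoglobin criterion is not commensurate with those beside it, and a minor extracranial bleed could be graded major on a fall that fluids may explain. The expected direction is a higher major-bleeding rate in the endovascular arm. The size of that inflation cannot be given, because the Protocol states neither a rate of minor access-site bleeding nor a distribution of haemoglobin change. The 2-10 g/L dilution range depends on the assumed baseline, blood volume, duration and retention; the mismatch in scale between 5 g/L and the other criteria is plain from the text and does not depend on them. This should be fixed, but it is confined to one safety outcome: symptomatic intracranial haemorrhage, the primary analysis and the sample size are unaffected.

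**What to change.** 1. Check the threshold and its unit against the sponsor's source definition, and correct them so that the haemoglobin criterion is of the same order of severity as the others. The documents do not settle the value, so the sponsor must.
2. State that the criterion applies only to clinically evident or imaging-confirmed extracranial bleeding, so that a change on the 24-hour CBC cannot qualify alone.
3. Use the corrected definition to fill the placeholder in Safety Outcomes (ii), and reconcile it with the synopsis item and the text under Process and Quality Outcomes, so that one outcome has one name and one definition.
4. Re-adjudicate any event already graded major on haemoglobin alone.

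The cost is a line or two in the Protocol, a matching change to the case report and adjudication forms, and review of any affected events. No new data are needed for the definition itself.
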